In this non-inferiority trial, we aim to compare technology-assisted community-based WGS result delivery by healthcare providers with formal genetic counseling by genetic counselors (GCs). The clinical trial will include parents/caretakers of newborns who undergo WGS. We estimate that 800 parents/caregivers will be enrolled into the clinical trial. Given the complexity of secondary findings and their implications, the parents of all children with secondary findings in the American College of Medical Genetics and Genomics (ACMG) gene list will be provided with formal genetic counseling (standard of care) and will thus be excluded from the clinical trial. We estimate that ~1.5% of sequenced probands will have such findings. Families enrolled before and after the trial period, (the trial is slated to end in January 2021, contingent on whether a no cost extension is to be awarded) will receive results from a GC.

3.e.1 Participant Randomization

Randomization will occur centrally once the WGS results are available and clinical summaries of results are created, ~45-90 days after enrollment, using a computer-generated random number generator. The unit of randomization will be at the family level. Permuted block randomization with varying block size will be utilized. Randomization will be stratified by site and type of WGS result (positive/inconclusive/no finding). Participating families will be assigned to one of the two study arms in a 1:1 ratio. The randomization status of a participant family will be communicated to a site at the same time that the results and clinical summary/family-friendly report are provided to the site, and the site is notified that results are ready to be returned. The Randomization Binder will be kept by [name], lead GC at HudsonAlpha, and will be communicated to the sites by uploading the result file within GG to the site coordinator and to the disclosing health care provider, if known. When files are uploaded, a note will be made of the randomization status. The randomization status of each case will also be documented and tracked in a secure, password-protected excel file outside of Genome Gateway, which will not be accessible to the rest of the study team.

3.e.2 Implementation of the Intervention

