The primary delivery mechanism for the educational content is the Genome Gateway web platform. Genome Gateway serves as the single source for participating families to review their designated learning topics. Participating families will be given an account and automatically assigned a series of brief learning topics at enrollment. HudsonAlpha genetic counselors will assign all additional learning topics (tailored based on results) manually after ROR at the same time that an electronic version of the result report and letter are uploaded to the participant's files. The topics will vary on the type of WGS result returned but will be assigned in a consistent manner across all patients. Each site has been provided with two iPads for the participating families to use for enrollment and viewing of the educational materials.

(2) Educational Materials/Training for the Healthcare Providers

Educational materials for the healthcare providers that will be involved in disclosing WGS results will be in the form of 1) in-person training, 2) materials hosted in Genome Gateway for enduring/just-in-time access.

A half-day in-person training will occur at each site prior to the launch of the clinical trial. Contents of this training will include background information and logistics about SouthSeq, WGS, Genome Gateway and the clinical trial. The majority of the training will focus on the delivery of WGS results. The training will consist of a few short didactic talks, hands on learning activities, small group discussion, and role-plays. Additional training sessions will be conducted remotely over the phone with a HudsonAlpha GC to allow providers to work through the training materials and care for patients, as well as onboarding of new study personnel when necessary. **A provider should not return results until fully onboarded (e.g. trained with the protocol).**

Fact sheets about each training topic have been developed as part of the training materials and are available for later reference (see appendix 6). All training materials will be organized and hosted within Genome Gateway and assigned to the healthcare providers for enduring access.

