- Disorders with established low genetic yield, e.g., gastroschisis, hydronephrosis, isolated congenital heart defects
- confirmed teratogenic exposure
- confirmed congenital infection

Patient experience

Logistics of return of results

Return of results is a process by which participant families, and the local clinical team, are notified about the findings of the genome sequencing test.

- Begins when a result report is ready
- Ends when the results have been documented in the medical record and communicated with the clinical team

From blood sample to result report

- Blood samples sent to HudsonAlpha for sequencing and analysis
- Any findings are confirmed in the lab by a second test
- Any findings are discussed at a Variant Review Committee (VRC) meeting
- HudsonAlpha genetic counselors translate decisions made at the VRC into patient-friendly result report letters

It doesn't end there...

- The lab at HudsonAlpha may learn new information about the results, and issue an updated report
 - Disclosed by the same provider who gave initial results
- The patient may experience new problems/symptoms that could be communicated to the lab
- The patient may have additional questions or concerns that need to be addressed

Where you come in...

```

graph TD
    A[Result Ready] --> B[Result Disclosure]
    B --> C[Documentation and Follow-Up]
    C --> A
  
```

Result Ready

- Letter and randomization status sent to site coordinator (in Genome Gateway)
- Will send to you as well, if we know who provider will be
- Will come from HudsonAlpha Genetic Counselor

Result Disclosure

- Appointment scheduled by site coordinator
- Family receives results from either GC or NICU provider (you)
- Family completes first post-result surveys with site coordinator

Documentation and Follow-Up

- You document disclosure in Genome Gateway
- You document disclosure at site (varies)
- You communicate result to clinical colleagues for follow-up — *moving result from research world back to clinical world*

The goal of this training is to equip you, the healthcare provider, with information, skills, and confidence to give genome sequencing results back to patients/families in the “experimental arm” of SouthSeq

Safety Nets

- HudsonAlpha GCs here to be a “just-in-time” resource for you throughout the study
- Specific patient situations that will automatically trigger disclosure by control arm (site genetic counselor)
 - i.e. secondary findings

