- Audio recording of result disclosures (all), monitoring and tracking of errors***

***Not meant to be anxiety inducing.

Result recording review

High-risk Safety Error

Errors in critical details that are likely to lead to patient harm

Ex. invasive testing recommended based on misinterpreted test result

Notify safety board; Real-time Feedback

Major Errors

Errors in critical details that are likely to have an impact on patient care and decision making

Ex. the recurrence risk is 25% (instead of <1%)

Real-time Feedback

Minor Errors

Errors in non-critical details that are unlikely to have an impact on patient care or decision making

Ex. this gene is on chromosome 6 (instead of 16)

End-of-study Feedback

Logistics, and some edge cases

Baby has been discharged prior to results	Come back to NICU to receive results in person
Baby has passed away prior to results	Come back to NICU to receive results in person
Family moves or is unwilling to return to NICU for results	Scheduled phone disclosure by same provider who would have done in-person disclosure, rest of process stays same
Family is completely lost to follow-up	Letter sent to family notifying of available results, results put in medical record

Questions?

Logistics of the trial

[figure not shown]

Study Population and Timeline

[figure not shown]
- ~1,100 families will be enrolled into the clinical trial
- Start of clinical trial
 - Site-dependent based on provider training
 - Onboarding of new sites
- Trial planned to end 6 months into year 4 (Jan. 2021)

SouthSeq - Workflow

SouthSeq Clinical Trial Flow

Hypotheses

Primary Hypothesis: No clinically relevant difference in the **parental empowerment** between the two arms (trained healthcare provider vs. genetic counselor)

Secondary Hypothesis: Trained health care provider arm will be non-inferior to the genetic counselor arm in terms of **personal utility** and **uncertainty**

[figure not shown]
$$X = Y$$

[figure not shown]
Take Away Messages

- The healthcare provider delivering results should not be the babies' current NICU attending MD/NP
 - The purpose of return of results does not include care/management of the condition (can discuss likely care changes/guidelines but not trigger that care during disclosure)
- Documentation by the healthcare provider to study staff about the disclosure session is critical to the fidelity of the trial
 - How disclosure was done
 - Who attended (which specific parents/caregivers)

Genome Gateway

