SLC25A13	200	200	137	Normal	WT/WT	Normal	Normal	Pathogenic
SLC25A13	200	200	138	Normal	WT/WT	Normal	Normal	Pathogenic
SLC25A13	200	200	139	Normal	WT/WT	Normal	Normal	Pathogenic
SLC25A13	200	200	140	Normal	WT/WT	Normal	Normal	Pathogenic
SLC25A13	200	200	141	Normal	WT/WT	Normal	Normal	Pathogenic
SLC25A13	200	200	142	Normal	WT/WT	Normal	Normal	Pathogenic
SLC25A13	200	200	143	Normal	WT/WT	Normal	Normal	Pathogenic
SLC25A13	200	200						

What you will not find in the result report

- Confirmation of paternity or non-paternity not reported by the study
- Consanguinity (parental relatedness) not reported by the study
- Secondary findings would automatically put the case in the control arm (for return by GC)

The result report/letter is your guide

Key talking points and take home messages

Resources to share with participant/family

Written in patient-friendly language

If you have questions...

Your HudsonAlpha GC:

[Birmingham: [name]; Jackson: [name]; Baton Rouge: [name]]

Genome Gateway messaging best and most secure communication method (can discuss PHI/clinical details).

Let's Practice...

- 6 example result reports, cover a wide range of possible results and implications
- Read result report as if you are preparing to disclose it to a family
 - Think about key messages, likely questions, if there is other information you want or need to gather prior to patient interaction
 - Highlight words/topics you want clarification on
 - Fill out chart
- Next will break up into small groups for in-depth discussion about the results with a genetic counselor

Psychosocial considerations in the context of genetics

Delivering Genomic Results

- Are genomic result disclosures different from other patient interactions? How?

Kaphingst, K. A., Ivanovich, J., Erick, A., Dresser, R., Matsen, C., & Goodman, M. S. (2016). How, who, and when: preferences for delivery of genome sequencing results among women diagnosed with breast cancer at a young age. *Molecular genetics & genomic medicine*, 4(6), 684-695.

Delivering Genomic Results

- Understanding the familial context of the result makes information more meaningful
- Counseling the family, not the result

Delivering Genomic Results

- Avoid information overload
 - Proceed slowly and divide up information

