Appendix 15: **Return of Results Workflow**

SouthSeq Result Return Workflow for Site Coordinators

Return of Results for Cases randomized to Standard of Care Arm (GC disclosure)

Preparation

1. Receive message within [Genome Gateway](#) from HA genetic counselor that a case has results ready to be returned and has been randomized to GC disclosure. Message will include participant ID. Site GC will also receive this message.
2. Review result report, attached to the message sent in Genome Gateway. Reach out to HA genetic counselor with any questions or concerns.
3. Return of result visit gets scheduled with primary parent contact. Depending on site-specific procedures this could be done by the GC, site coordinator, or administrative support. Encourage in-person disclosure if possible. At this time, confirm that the participant's address has not changed. If it has, please update it in the demographics section of Genome Gateway and have them complete a new W9 form. The new W9 should be uploaded to the participants account and to the "Clinical Trial" account in Genome Gateway.

Disclosure (via phone)

1. Site genetic counselor will call the primary parent contact at the scheduled time.
2. RESULTS ARE DISCLOSED by the site genetic counselor.
3. Site genetic counselor will be in communication with you during the disclosure to let you know if they successfully connected with the family and when the conversation is finished.
4. Once result disclosure is in process, log into Genome Gateway and assign the "In-clinic Survey" and "At-Home Survey" to the participant.
5. Site genetic counselor will transfer the call to you when disclosure is over, if you are available. If you are not available at that time, call the primary parent contact back within the next 72 hours. Attempt to reach multiple times if no answer.
6. Over the phone, have primary parent contact complete the "In-clinic survey" by asking the questions and marking their response on a paper version of the survey. The paper survey should then be scanned and uploaded to the participant's account and to the Clinical Trial account. If the participants decide not to do the survey over the phone, please remind them to log into Genome Gateway to complete them and remind them that compensation will be provided for completed surveys.
7. Discuss next steps in SouthSeq for family to expect (see below "Next Steps" list).

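### Section 3.e excludes families with an ACMG secondary finding from the trial, but the provider training puts them in the control arm; the two rules must be reconciled and the analysis set limited to randomised families.

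*Combined protocol and SAP*

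**What the plan says.** Section 3.e (Study Intervention) says that parents of children with ACMG secondary findings "will be provided with formal genetic counseling (standard of care) and will thus be excluded from the clinical trial". It puts their frequency as follows: "We estimate that ~1.5% of sequenced probands will have such findings". The same section says that families enrolled before or after the trial period also receive results from a GC.

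Appendix 6 (provider training) says otherwise on two slides. The slide on what the result report leaves out reads: "Secondary findings would automatically put the case in the control arm (for return by GC". The Safety Nets slide gives secondary findings as its example of "Specific patient situations that will automatically trigger disclosure by control arm (site genetic counselor". The training reaches all sites (3.e.3): "A half-day in-person training will occur at each site prior to the launch of the clinical trial".

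Section 3.e.1 places randomisation centrally, after the sequencing results and clinical summaries exist, at 1:1, stratified by site and by positive, inconclusive or no finding. It does not say that the secondary-finding check comes before the draw. The return procedures in Appendix 15 are organised by randomised arm, for example "Return of Results for Cases randomized to Standard of Care Arm (GC disclosure", and contain no path for a GC return outside the trial.

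The SAP compares mothers randomised to each type of provider. It defines no analysis set and does not mention secondary findings.

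**The concern.** Being excluded and being placed in the control arm are different trial statuses. Under 3.e the family leaves the comparison. Under the slides it is counted with the GC arm although no draw was made, and it could never have been in the provider arm.

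Membership would then depend on the content of the result, and randomisation cannot balance that. The strata do not help, because a secondary finding can accompany any primary result. Appendix 1, for instance, has a sample report with a negative primary result and a positive *APOB* secondary result.

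At stake is the GC-minus-provider difference in means, on which all three non-inferiority tests rest.

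**Working it through.** **1. The plan's own figure.** PRU in the SAP: GC 78.40 (SD 20.51), provider 73.93 (SD 19.86), difference 4.47, upper 97.5% bound 10.13, margin 10, p = 0.0277. The documents give no analysed numbers, so I solved for an equal n per arm:

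- Sum of squared SDs: 20.51² + 19.86² = 420.66 + 394.42 = 815.08.
- n = 1.972² × 815.08 / (10.13 − 4.47)² ≈ 99 per arm.
- SE = √(815.08/99) = 2.869; bound = 4.47 + 1.972 × 2.869 = 10.13.
- t = (10 − 4.47)/2.869 = 1.927 on 196 df, p = 0.0277.

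The stated bound and p-value agree with each other at this n. The same method gives about 96 per arm for GCOS and about 100 for PUGS, with p < 0.0001 for both, as stated.

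**2. Number of families.** Section 3.e: "We estimate that 800 parents/caregivers will be enrolled into the clinical trial". At 1.5% that is 0.015 × 800 = 12.

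- Under 3.e: 788 randomised, 394 v 394.
- Under the training rule: 394 + 12 = 406 v 394, so 12/406 = 2.96% of the GC arm is not randomised.

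The training slides give another size, about "1,100 families will be enrolled into the clinical trial". That yields 16.5 families and the same share: 16.5/(541.75 + 16.5) = 2.96%. Among the roughly 198 families implied for PRU, 1.5% is about 3.

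**3. Gap needed to reverse a conclusion (SE held fixed).** If these families differ from the other GC families by D, the GC mean moves by 0.02956 × D.

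| Outcome | Bound | Margin | Distance | D needed | Scale span |
|---|---|---|---|---|---|
| GCOS | 4.83 | 10 | 5.17 | 175 | 24 × 6 = 144 |
| PUGS | 1.22 | 3.5 | 2.28 | 77 | 8 × 4 = 32 |
| PRU | 10.13 | 10 | 0.13 | 4.4 | – |

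For GCOS and PUGS, D exceeds the whole scale. As a deliberately extreme check, suppose all 12 families expected among 800 were in the analysed GC group. D would then be 5.17/(12/96) = 41 points on GCOS (3.0 of the reported GC SDs) and 2.28/(12/100) = 19 points on PUGS (2.6 SDs).

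**4. PRU with three GC families removed (SDs unchanged).** Let d be their excess over the overall GC mean:

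- Bound = 4.47 − 3d/96 + 1.9723 × √(420.66/96 + 394.42/99) = 10.175 − 3d/96.
- This equals 10 at d = 0.175 × 32 = 5.6.
- Measured against the other GC families, the gap is 5.6 × 99/96 = 5.8 points, or 5.8/20.51 = 0.28 SD.
- At d = 10 the bound is 9.86. At d = 0 it is 10.175, and if the three scored lower it rises further.

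**The case against.** The strongest reply is that the slides are shorthand for who discloses the result. The first adds in parentheses that the return is by a GC, and the second speaks of disclosure. The audience is NICU providers, who allocate no one. The slides are also not the controlling text, as their different trial size shows. Section 3.e states the exclusion, the draw is central and made after results are known, and the SAP speaks of randomised mothers.

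Much of this stands. The shorthand reading is plausible, and the other texts lean towards exclusion. It does not settle the matter. Study genetic counselors teach much of the programme, and the lead genetic counselor at HudsonAlpha keeps the randomisation binder, so the wording is not confined to people with no part in allocation. No text says that the check precedes the draw, and the SAP defines no analysis set.

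Three further inferences are tempting but unsupported:

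- *Families who take sequencing but decline the trial also enter through GC disclosure.* Section 3.c.2 names no discloser for them and says that they decline randomisation and surveys.
- *The exclusion should have been in the 3.c.2 criteria or the screening log.* Both apply at enrolment, before a secondary finding can be known.
- *Appendix 15 sweeps non-randomised families into the control arm.* Its headings refer to randomised cases. The missing path is a gap and does not show that anyone was counted.

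**Conclusion.** The contradiction is real and concerns trial membership. If the training rule reached the tracking file, about 3% of the GC arm would be non-randomised, in one direction only. The change should be made, but the primary conclusion does not depend on it: at the plan's 1.5%, neither the GCOS nor the PUGS conclusion could be reversed.

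PRU is the exception, because it missed its margin by only 0.13. A reader might infer that such families caused the miss. The documents do not support that. They do not show that any were analysed, and the SAP's wording, applied strictly, leaves them out. The reversal is a scenario resting on a back-solved n of about 99, equal arms, unchanged SDs, three such families present, and scores about 5.8 points or more above the other GC families. With lower scores, removing them would widen the miss.

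**What to change.** - Reword the two Appendix 6 slides to match 3.e: a secondary finding takes the family out of the trial, a GC returns the result (as both texts already say), and no arm is assigned.
- State in 3.e.1 that the secondary-finding check precedes the random draw.
- In the tracking file, give these families and those enrolled outside the trial period a separate status such as *GC return, not randomised*.
- Limit the SAP analysis set to families with a randomisation record, and report how many secondary-finding families, if any, were in the GC data set. If there were any, repeat the three tests without them.

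The cost is wording on two slides, one sentence, one status code, one data filter and one database count. No extra families, visits or surveys are needed.

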Appendix 7: Survey Measures by Time Point

Appendix 7.1
Enrollment Survey

1. *Please identify the individual completing this survey.

- Mother
- Father
- Other (please specify): _____

2. *What is your age?**3. *Do you speak another language besides English? (Check one)***

- Yes (**If marked, complete next 2 questions**)
- No

- How well do you speak English?

- Native English-speaker
- Very well
- Well
- Not well

- What language do you prefer to speak with your child's doctors?

- English
- Another language (**If marked, please select language from the list below**)
- I am equally comfortable discussing my child's medical care in both English and another language

- Please tell us which language you prefer to speak with your child's doctors:

- Spanish
- Vietnamese
- Chinese (Mandarin, Cantonese, or other Chinese language)
- Tagalog
- German
- French
- Korean
- Russian
- Arabic
- Other (please specify): _____

4. *What category or categories best describe you? Check all that apply.

- American Indian, Native American, or Alaskan Native
- Asian
- Black or African American
- Native Hawaiian/Pacific Islander
- White or European American
- Middle Eastern or North African/Mediterranean
- Hispanic/Latino(a)
- Prefer not to answer

Unknown/None of these fully describe me

5. ***What category or categories best describe your child? Check all that apply.**

- American Indian, Native American, or Alaska Native
- Asian
- Black or African American
- Native Hawaiian/Pacific Islander
- White or European American
- Middle Eastern or North African/Mediterranean
- Hispanic/Latino(a)
- Prefer not to answer
- Unknown/None of these fully describe my child

6. ***Are you currently (please select one):**

- Married
- Living together but not married
- Separated or Divorced
- Widowed
- Never married and currently not living together

7. ***What is your employment status from this past week? (check all that apply)**

- Working for pay at a job or business
- With a job or business but not at work
- Looking for work
- Working, but not for pay, at a family-owned job or business
- Not working at a job or business
- Not looking for work
- Taking care of house or family
- Going to school
- Retired
- Disabled
- Other: _____
- Prefer not to answer
- Don't know

8. ***What was your household's total family income (before taxes) from all sources in the last year? (Check one)**

- Less than \$10,000
- \$10,000 to \$14,999
- \$15,000 to \$19,999
- \$20,000 to \$24,999
- \$25,000 to \$29,999
- \$30,000 to \$39,999
- \$40,000 to \$49,999
- \$50,000 to \$59,999

- \$60,000 to \$69,999
- \$70,000 to \$79,999
- \$80,000 to \$99,999
- \$100,000 to \$119,999
- \$120,000 to \$139,999
- \$140,000 or more
- Prefer not to answer

9. How many people (children and adults) were supported by this income in the last year?

10. *What is the highest grade or level of school you completed or the highest degree you received? (Check one)

- No schooling completed
- Elementary school (kindergarten through 5th grade)
- Middle school (6th, 7th, or 8th grade)
- Some high school (9th, 10th, or 11th grade)
- 12th grade, no diploma
- High school graduate (diploma or GED or equivalent)
- Some post-high school training (college or occupational, technical, or vocational training), no degree or certificate
- Completed occupational, technical, or vocational program, received degree or certificate
- Associate (2-year) college degree
- Bachelor's degree (for example: BA, AB, BS)
- Master's degree (for example: MA, MS, MEng, MEd, MSW, MBA)
- Professional degree (for example: MD, DDS, DVM, LLB, JD)
- Doctoral degree (for example: PhD, EdD)

11. *Are you covered by health insurance or some other kind of health care plan? (Include health insurance obtained through employment or purchased directly, as well as government programs like Medicare and Medicaid that provide medical care or help pay medical bills) (Check one)

- No
- Yes

12. If you answered yes for #11: What kind or kinds of health insurance or health care coverage do you have? (Check all that apply)

- Private health insurance, employment based
- Private health insurance, directly purchased
- Government plan, Medicare
- Government plan, Medicaid
- Government plan, Military health care
- Other type of insurance (Please Describe): _____

No coverage of any type.

13. *Is your child covered by health insurance or some other kind of health care plan?

(Include health insurance obtained through employment or purchased directly as well as government programs like Medicare and Medicaid that provide medical care or help pay medical bills) (Check one)

No
 Yes

14. If you answered yes for #13: IF YOUR CHILD IS COVERED: What kind or kinds of health insurance or health care coverage do they have? (Check all that apply)

Private health insurance, employment based
 Private health insurance, directly purchased
 Government plan, Medicare
 Government plan, Medicaid
 Government plan, Military health care
 Other type of insurance (Please Describe): _____
 No coverage of any type.

15. *Which of the following currently applies to your child?

[figure not shown]
My child is currently in the hospital
 My child is now living outside the hospital
 My child is no longer living (**if selected, skip to Question 17**)

16. How good is your child's health TODAY?

- We would like know how good or bad your child's health is **TODAY**.
- This line is numbered **0** to **100**.
- **100** means the best health you can imagine. **0** means the worst health you can imagine.
- Mark an X on the scale to indicate how your child's health is **TODAY**
- Now please write the number you marked on the scale in the box below

YOUR CHILD'S HEALTH TODAY= _____

- **N/A**

17. *Considering your child's medical condition, please rank the degree to which you agree with the following statements:

	Strongly Disagree	Disagree	Somewhat Disagree	Neutral	Somewhat Agree	Agree	Strongly Agree
I am clear in my own mind why my family has enrolled in SouthSeq.							
I can explain what the condition means to people in my family who may need to know.							
I understand the impact of the condition on my child(ren)/any child I may have.							
When I think about the condition in my family, I get upset.							
I don't know where to go to get the medical help I/my family need (s).							
I can see that good things have come from having this condition in my family.							
I can control how this condition affects my family.							
I feel positive about the future.							
I am able to cope with having this condition in my family.							
I don't know what could be gained from each of the options available to me.							
Having this condition in my family makes me feel anxious.							
I don't know if this condition could affect my other relatives (brothers, sisters, aunts, uncles, cousins).							

In relation to the condition in my family, nothing I decide will change the future for my children/any children I might have.							
I understand the reasons why my child's doctor referred my family to SouthSeq							
I know how to get the non-medical help I/my family need(s) (e.g. educational, financial, social support).							
I can explain what the condition means to people outside my family who may need to know (e.g. teachers, social workers).							
I don't know what I can do to change how this condition affects me/my children.							
I don't know who else in my family might be at risk for this condition.							
I am hopeful that my child(ren) can look forward to a rewarding family life.							
I am able to make plans for the future.							
I feel guilty because I (might have) passed this condition on to my children.							
I am powerless to do anything about this condition in my family.							
I understand what concerns led to my referral to SouthSeq							
I can make decisions about the condition that may change my child(ren)'s future/the							

future of any child(ren) I may have.						
---	--	--	--	--	--	--

18. For each item, rate yourself on the scale from “Not at all Good (1) to Extremely good (6)”

a. How good are you at working with fractions?

Not at all good					Extremely Good
1	2	3	4	5	6

b. How good are you at figuring out how much a shirt will cost if it is 25% off?

Not at all good					Extremely Good
1	2	3	4	5	6

c. How often do you find numerical information to be useful?

Never					Very often
1	2	3	4	5	6

19. *Please mark the following statements as True or False.

	True	False
It is possible to see a gene with the naked eye.		
Healthy parents can have a child with a hereditary disease.		
The onset of certain diseases is due to genes, environment and lifestyle.		
The carrier of a disease gene may be completely healthy.		
All serious diseases are hereditary.		
Genes are inside cells.		
The child of a disease gene carrier is always also a carrier of the same disease.		
A gene is a piece of DNA.		
A gene is part of a chromosome.		
All body parts have all of the same genes.		
It has been estimated that a person has about 20,000 genes.		
A person's race and ethnicity can affect how likely they are to get a disease.		
Each of us has variations in our genes that make it more likely that we will get certain diseases.		
A “complex disease” is a health condition brought on by many genes and lifestyle and environment.		
A single nucleotide polymorphism or “SNiP” is a variation present in some individuals that stretches across a large section of DNA.		

20. Rate how certain you anticipate feeling about the following aspects of your child's upcoming sequence results:

	Very Uncertain (1)	2	3	4	Very Certain (5)
What my child's future test results may mean for his/her health					
What future actions I will need to take based on my child's test results					
How my child's physician may use the future results to improve my child's health					
Whether I will be worried or concerned about my child's future test results					
Whether my child's future test results will reveal something alarming					
Whether my child's future test results will disrupt my child's life					
Whether I will be able to trust my child's future test results					
Whether my child's future test results will be accurate					

21. *Please rank the degree to which you agree with the following statements

	Always	Often	Sometimes	Occasionally	Never
How often do you have someone (like a family member, friend, hospital/clinic worker, or caregiver) help you read medical materials?					
How often do you have problems learning about your medical condition because of difficulty reading written information?					
How often do you have a problem understanding what is told to you about your medical condition?					
	Not at all	A little bit	Somewhat	Quite a bit	Extremely
How confident are you filling out forms by yourself?					

22. *In general, would you say your health is:

Excellent	Very Good	Good	Fair	Poor

23. *Here are some questions about the support that is available to you.

a. About how many close friends and close relatives do you have (people you feel at ease with and can talk to about what is on your mind)?

Write in number of close friends and close relatives: _____

b. People sometimes look to others for companionship, assistance, or other types of support. How often is each of the following kinds of support available to YOU if you need it?

	None of the time	A little of the time	Some of the time	Most of the time	All of the time
Someone to help you if you were confined to bed...					
Someone you can count on to listen to you when you need to talk...					
Someone to give you good advice about a crisis...					
Someone to take you to the doctor if you needed it...					

Someone who shows you love and affection...					
Someone to have a good time with...					
Someone to give you information to help you understand a situation...					
Someone to confide in or talk to about yourself or your problems...					
Someone who hugs you...					
Someone to get together with for relaxation...					
Someone to prepare your meals if you were unable to do it yourself...					
Someone whose advice you really want...					
Someone to do things with to help you get your mind off things...					
Someone to help with daily chores if you were sick...					
Someone to share your most private worries and fears with...					
Someone to turn to for suggestions about how to deal with a personal problem...					
Someone to do something enjoyable with...					
Someone who understands your problems...					
Someone to love and make you feel wanted...					

